Part C will evaluate 111 subjects total (37 per treatment arm) aged ≥ 1 month to ≤ 36 months with an aim to have at least 34 evaluable subjects per treatment group. The primary endpoint will be the time-weighted average change from Baseline to Day 7 in RSV viral load measured in nasopharyngeal swabs by RT-qPCR comparing two dose levels of RV521 vs. placebo. Secondary endpoints will assess the safety, and efficacy of two dose levels of RV521 vs. placebo. Dose levels in Part C will be selected following the analysis of PK data, tolerability and safety from Part B. Two doses (RV521 age group specific high dose and RV521 age group specific low dose) will be selected for inclusion in Part C. The high dose will be selected for each age group to target approximately 90% of subjects achieving the target trough concentration for efficacy (3x EC₉₀), while not exceeding the upper safety limit, based on the paediatric PK model. The low dose will be selected such that the target trough level of 3xEC₉₀ is achieved in approximately 75% of the subjects. The high dose may be the highest tolerated dose from Part B, or a higher twice daily dose of RV521, depending on the safety, tolerability and PK data from Part B.

Subjects in Part C will be stratified by age (≥ 1 to < 6 months of age vs. ≥ 6 months to ≤ 36 months of age) and randomised in a 1:1:1 ratio. Both age strata will be enrolled in parallel. To maintain the double-blind, subjects randomised to placebo will be allocated to low volume (to match the volume associated with the lowest tested dose of RV521) or the higher volume (to match the highest tested dose of RV521).

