8.5.4 Method of Assigning Subjects to Treatment Groups

Part A:

Part A of the study is open-label and all subjects will receive RV521. The dose to be received by a given subject will be the dose currently being investigated, at the time the subject is enrolled, in the applicable cohort, as described in [Section 8](#).

Part B and Part C:

In Parts B and C, subjects will be randomised to treatment according to a central randomised list for each cohort. To protect the blind, the list will be produced by an unblinded biostatistician at Syneos Health who will be independent of the blinded statistician.

For Part B, subjects in Cohorts 3 and 4 will be randomised to RV521 or placebo (3:1). The randomisation list for Cohort 5 will be designed to ensure that the subjects who contribute to the final recruitment total of 24 are randomised to receive RV521 or placebo (2:1). The dose to be received by a given subject will be the dose currently being investigated at the time the subject is enrolled, in the applicable cohort, as described in [Section 8.1](#).

For Part C Cohort 6, the randomisation list will be designed such that the total of approximately 111 subjects (37 subjects per treatment group) will be randomised with an aim to have at least 34 evaluable subjects included in the analysis of viral load. Randomisation will be stratified by age

group (≥ 1 month to < 6 months vs. ≥ 6 months to ≤ 36 months) to ensure balance across the treatment groups, but there is no specified number of subjects that will be required in each stratum. Subjects will receive RV521 (age group specific low or high dose level) or placebo in a 1:1:1 ratio. Subjects randomised to placebo will be allocated randomly to either a low dose volume or a high dose volume to maintain the integrity of the double-blind design.

At the time of randomisation, a subject will be sequentially assigned to the next available treatment from the randomisation list for that cohort and stratum. Randomisation will be performed using an interactive web response system (IWRS). A blinded treatment kit (or > 1 kit, if required, in Part B and Part C), corresponding to the randomised treatment, will be allocated to each subject.

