The Overall Time to Improvement will be defined as the time from randomisation to the time that all RSV-related signs and symptoms are mild or absent. The overall time to improvement will be summarised for each treatment group by mean, median, SD, minimum and maximum and 95% confidence intervals.

Overall Time to Resolution of RSV-related signs and symptoms will be calculated from the time of randomisation to the time that they are no longer present (absent), and will be summarised and analysed as for Time to Improvement.

Treatment groups will be compared for differences in overall severity assessed by the composite symptom score on each day whilst hospitalised and at follow-up visits.

For Part C, time to resolution of symptoms will be compared between each dose level of RV521 and Placebo using a generalised Wilcoxon Rank test. Details of the analysis will be provided in the SAP.

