### 8.1. RSV Clinical Scoring System Score

The RSV Clinical Scoring System gives a score from 0 to 12.

For each of Parts A, B and C, the RSV Clinical Scoring System score will be summarised at baseline and at each post-baseline time point. Summary statistics will be provided for the observed values and the corresponding changes from baseline for post-dose assessments. Plots of the mean  $\pm$  SD observed and change from baseline RSV Clinical Scoring System score by time point (baseline and each post-baseline assessment) will be presented. If necessary, lower SD bars will be truncated at 0 for the observed value plot.

For Part B, comparisons will be made between RV521 and placebo using a mixed effects analysis of covariance (ANCOVA) model on the change from baseline in RSV Clinical Scoring System score including a random effect term for subject, fixed effect terms for treatment group, age group ( $\geq 1$  month to  $< 6$  months or  $\geq 6$  months to  $\leq 36$  months at screening), visit and visit by treatment group interaction, and baseline RSV Clinical Scoring System score as a covariate. The model will be fitted to the 24 subjects treated at the final doses selected for Cohort 5 (see Section 6.1).

For Part C, comparisons will be made between RV521 and placebo using a mixed effects ANCOVA model on the change from baseline in RSV Clinical Scoring System score including a random effect term for subject, fixed effect terms for treatment group, visit, visit by treatment group interaction, duration of symptoms prior to randomisation and severity of illness at randomisation, and baseline RSV Clinical Scoring System score as a covariate.

For each model, a point estimate and 95% confidence interval will be calculated for the mean difference between RV521 and placebo.

Distributional assumptions underlying the statistical analyses will be assessed by visual inspection of residual plots. Normality will be examined by normal probability plots, while homogeneity of variance will be assessed by plotting the residuals against the predicted values for the model. If the distributional assumptions of a normal distribution in the parametric approach are not satisfied, investigations into influence of outliers or non-parametric methods will be considered.

In addition, for each of Parts A, B and C, the RSV Clinical Scoring System score will be categorised as:

- Mild – scores  $\leq 5$ .
- Moderate – scores  $> 5$  and  $< 9$ .
- Severe – scores  $\geq 9$ .

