## 8.3. RSV-related Signs and Symptoms

RSV-related signs and symptoms (temperature, respiratory rate, coryza, cough, grunting with expiration, nasal flaring, retractions, wheezing and SpO2 on Room air) will be collected on the CRF at each time point identified in the Schedule of Assessments for Part B (Table 2), and Part C (Table 3) in Section 3.10.

For study Parts B and C, assessments of individual RSV-related signs and symptoms will be summarised at each time point. For quantitative variables, observed values and changes from baseline will be summarised. In addition, highest level of severity during the study for each individual RSV-related sign and symptom will be summarised using summary statistics for categorical variables.

Time to improvement will be calculated for RSV-related signs and symptoms that are classified as moderate or severe during the course of the study and will be defined as the time from randomisation until no longer present (absent or severity=0) or mild. If there is no improvement, then time to improvement will be censored as the date/time RSV-related signs and symptoms were last recorded. Time to improvement will be summarised (number [%] of subjects analysed, mean, median, SD, minimum, maximum) for Parts B and C. The overall time to improvement will be defined as the time from randomisation to the time that all RSV-related signs and symptoms are mild or absent. The overall time to improvement will be summarised for Parts B and C by n, mean, median, SD, minimum, maximum and 95% confidence intervals for the mean. For Part C only, time to improvement of symptoms and overall time to improvement, will be compared between RV521 and Placebo using a Generalised Wilcoxon analysis, which is a weighted log-rank test, weighted by the number of subjects at risk immediately prior to the event, and will include duration of symptoms prior to randomisation as a covariate. Also for Part C only, Kaplan-Meier plots for time to improvement of symptoms and overall time to improvement will be presented by treatment.

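### Part C is randomised by age stratum, but the Part C clinical tests detailed in SAP v2.0 leave age out; if age is prognostic, they are conservative and lose power

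*Protocol*

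**What the plan says.** **Randomisation.** The protocol synopsis states: "Subjects in Part C will be stratified by age", split at 6 months. Section 8.5.4 says this is done "to ensure balance across the treatment groups", "but there is no specified number of subjects that will be required in each stratum". It adds: "Subjects will receive RV521 (age group specific low or high dose level) or placebo in a 1:1:1 ratio". No other stratification factor is named.

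**Time to resolution.** Protocol 11.1.5 says "time to resolution of symptoms will be compared between each dose level of RV521 and Placebo using a generalised Wilcoxon Rank test". It names no covariate or strata, and its next sentence leaves the details to the SAP. SAP 8.3 specifies for Part C a generalised Wilcoxon analysis that "will include duration of symptoms prior to randomisation as a covariate". It sets this out for time to improvement and then applies the same analysis to time to resolution.

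**Symptom scores.** Protocol 11.1.5 says only that analysis of covariance will be used. The Part C model in SAP 8.1 has treatment group, "visit, visit by treatment group interaction, duration of symptoms prior to randomisation and severity of illness at randomisation", plus baseline score and a random subject effect. The Part B model in the same section is specified as "including a random effect term for subject, fixed effect terms for treatment group, age group" and further terms. SAP 8.2 carries the 8.1 models over to the parental ReSVinet scale.

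**Age elsewhere.** For the Part C clinical endpoints, age appears in the SAP only as a subgroup display (6.6).

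**SAP status.** SAP 3.5 and 3.8.1 describe Part C as 1:1 with about 120 subjects, stratified by symptom duration and clinical score. Protocol 11.1 allows SAP amendments for Part C up to database lock and unblinding.

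**The concern.** Stratified allocation makes the arms alike on age, so the treatment difference no longer carries chance age imbalance. A test that ignores the strata still counts the between-age spread as random error. Its standard error is then too large: the true alpha falls below 5%, and a real effect is easier to miss than in an analysis that uses the strata.

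What is at stake is power for the clinical endpoints of Part C (time to resolution, time to improvement, and the clinician and parental scores). In the current protocol these are secondary.

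**Working it through.** **1. The plan's own figure.** Protocol 11.2 gives 34 per group, a difference of 1 log10, SD 1.25 and two-sided alpha 0.05. Power = Φ(0.8 × √(34/2) − 1.96) = Φ(1.34) = 91.0%; the t-test version gives 90.2%. The stated 90% reproduces, but it belongs to the viral-load endpoint. The current protocol states no power for the clinical tests.

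**2. Spread of resolution times.** SAP 3.7 gives a median of 15 days and an interquartile range of 9 days. That section belongs to the older Part C design, but it is the only source in the documents. For log-normal times, 9 = 30 × sinh(0.6745σ), so σ = asinh(0.3)/0.6745 = 0.438.

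**3. Closed form for alpha.** Take two equal strata whose medians differ by a ratio r, with the total log-SD held at σ. Age then explains R² = (½ ln r)²/σ². The actual alpha of the unstratified test is 2 × [1 − Φ(1.96/√(1 − R²))].

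- r = 1.3: R² = 0.1312²/0.438² = 0.090; alpha 4.0%
- r = 1.5: R² = 0.2027²/0.438² = 0.214; alpha 2.7%
- r = 1.8: R² = 0.2939²/0.438² = 0.45; alpha 0.8%

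**4. Simulation.** 34 per arm, balanced strata, uncensored times, σ = 0.438, 20,000 trials per setting. Power is shown as unstratified vs stratified Wilcoxon.

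| Ratio of medians (assumed) | Actual alpha, unstratified | Power, 20% reduction | Power, 25% reduction |
|---|---|---|---|
| 1.0 | 5.0% | stratifying costs 0.7–0.9 points | – |
| 1.3 | 4.0% | 52% vs 55% | – |
| 1.5 | 2.7–2.9% | 52% vs 61–62% | 76–77% vs 83% |
| 1.8 | 0.7–0.8% | 49–50% vs 77–78% | – |

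**5. Sensitivity.**

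- *Wider spread.* With σ = 0.8 and r = 1.5, R² = 0.2027²/0.8² = 0.064 and alpha is 4.3%. Power for a 25% reduction is 29% vs 31%.
- *Follow-up visits only at Days 7, 14 and 34 after dosing.* With r = 1.5 and a 20% reduction, power is about 42% vs 51%.
- *Censoring.* 37 per arm, 10% random dropout, censoring at Day 34, log-SD 0.438 within each stratum, 25% reduction. Power is 77.1% vs 76.7% at r = 1.0, 74.9% vs 76.1% at 1.25, 70.0% vs 76.3% at 1.5 and 56.0% vs 76.3% at 2.0. With a 30:70 age split and r = 1.5 it is 70.4% vs 75.2%.

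**6. Score model.** Covariance analysis at a single visit, 37 per arm, effect set for about 80% power:

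| R² for age given baseline score (assumed) | Actual alpha without age | Power without vs with age |
|---|---|---|
| 0 | 4.9% | 79.6% vs 79.5% |
| 0.05 | 4.6% | 79.6% vs 81.0% |
| 0.10 | 3.9% | 80.7% vs 83.6% |
| 0.20 | 2.9% | 81.3% vs 87.1% |

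**7. Could age be prognostic?** The documents give no estimate, but one feature points that way. Respiratory rate is among the signs collected (Protocol Appendix 17.4). Section 10.1.3.7 classes a rate as normal in Part C only at 30 breaths/min or below, at every age. The clinician scale in Appendix 17.6 gives normal ranges of 40–50 below 2 months and 35–45 at 2–6 months. If the fixed cut-off decides resolution, a recovered young infant may not count as resolved. If that blocked 30% or 60% of the younger stratum (assumed shares), alpha would be 4.3% or 2.5%, and power for a 25% reduction 51% vs 53% or 23% vs 37%.

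**The case against.** **The protocol does not prescribe an unstratified test.** A reader might infer that it does. Section 11.1.5 names the test and defers the rest, and for the scores it lists no covariates. This stands: the omission is in the SAP.

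**SAP v2.0 describes a different Part C.** Its score model carries both factors of its own randomisation, so it was not careless for that design, and an amendment is already provided for. This stands as to the cause. It does not remove the need for an explicit instruction: even under the older design, the Wilcoxon test carried only one of the two stratification factors, so aligning the design text would not by itself bring age in.

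**The SAP 8.1 score is no longer used in Part C.** Protocol 11.1.5 assigns the RSV Clinical Scoring System to Parts A and B and the ReSVinet scale for clinicians to Part C. Correct: a new model has to be written, not the old one patched.

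**The Part B model is weak evidence of an oversight.** SAP section 15 drops dose from that model because dose coincides with age group there, so age also stands in for dose. Nor do age-specific doses in Part C show that age is prognostic, since Protocol 8.2 aims for equal exposure in the two age groups. Both points stand.

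**The loss may be small.** It vanishes if age has no effect, is about 2 points at a 1.5-fold gap with log-SD 0.8, and may be partly absorbed by baseline score in the score model. The symptom-duration covariate was not simulated. All of this stands, and it is why the size is given as a range.

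**Conclusion.** The concern holds conditionally. The current protocol stratifies Part C by age alone, and the only detailed Part C clinical analyses available contain no age term. If age is prognostic, those secondary-endpoint tests are conservative and less powerful than an age-stratified analysis. For time to resolution the loss runs from about nothing, through roughly 3 points (1.3-fold gap) to about 10 points (1.5-fold gap, 20% reduction, log-SD 0.438), and more beyond that. These figures rest on assumed age gaps, log-normal times and a spread taken from the older design.

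Three stronger readings are not supported. The tests are not shown to run below 5%, because no age effect is documented. Type I error is not inflated, because the departure is in the conservative direction. No stated power is missed, because the current protocol gives none for these endpoints.

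**What to change.** In the Part C SAP amendment, signed off before database lock and unblinding:

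- Stratify the generalised Wilcoxon tests for time to resolution and time to improvement by the age stratum used at randomisation, and state how symptom duration is carried alongside it.
- Write Part C mixed models for the ReSVinet scale for clinicians and the parental ReSVinet scale with the randomised age stratum as a fixed effect.
- The Part C viral-load (DAVG) model in SAP 10.2.1 also lacks age and can be corrected in the same amendment.

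A clause in Protocol 11.1.5 naming the age stratum would keep the two documents aligned. The cost is wording only. No new data are needed, and if age turns out not to matter the stratified Wilcoxon test gives up less than one power point.

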11.1.6 Safety Variables

Adverse events will be coded according to the current version of MedDRA. Summary tables of AEs will be based on TEAEs, defined as events starting, or worsening, after the first dose of IMP. Summaries, by MedDRA SOC and Preferred Term, will be provided for all TEAEs, all treatment-related TEAEs (with causality assessed as possibly, probably or definitively related to IMP), all serious TEAEs and all AEs leading to early discontinuation from the study. Summary tables by maximum severity and maximum relationship, and by intensity per CTCAE will be presented.

For laboratory tests, ECG measures and vital signs parameters, baseline will be defined as the last non-missing result prior to the first dose of IMP. Results at each visit will be summarised using the statistics: n (number of observations), mean, SD, median, minimum and maximum. In addition, change from baseline from all safety parameters will also be summarised by post-baseline visits.

11.1.7 Interim Analyses

No formal interim analyses will be conducted. Each of Parts A, B and C will be reported separately and no pooling of Parts will occur.

Following review of Part B, a decision will be made regarding the dose levels to be investigated in Part C.

Note: Part C data will be analysed separately to the Part B data. Data will not be combined across Parts B and C, and therefore, the analysis of Part B has no impact on the type I error.

11.2 Determination of Sample Size

Because of the exploratory nature of the study, a formal sample size calculation has not been performed for Parts A and B. Twenty-four subjects enrolled in Part B and receiving RV521 or placebo (2:1) at the same dose level and according to the same dosing regimen for their specified age range group are expected to be sufficient to assess safety, PK, and antiviral data.

For an anti-viral effect (Part B), measured as a difference in viral load at a specific time point, and using data from the human challenge model (Study CCI [REDACTED]), 24 subjects split 16/8 would have 69% power to identify a difference of 2 log units, 87% power for a difference of 2.5 log units and 96% power for a difference of 3 log units.

Estimates for total enrolment into Part C are based on the report by [Cunningham et al \(2021\)](#); an assumed time-weighted average change in RSV log₁₀ viral load from baseline to day 7 in the placebo group of -1.5 log₁₀ vp/ml, with a standard deviation of 1.25. A sample size of 34 per group will provide 90% power to detect at least 1 log₁₀ decrease in RV521 groups using a 2-sided significance level of 0.05. To account for potential drop outs, an additional 10% will be added to give group size of 37 (total 111 subjects randomised 1:1:1; 2 dose levels of RV-521 vs. placebo).

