19. Any other reason which in the opinion of the Investigator makes the participant unsuitable for a clinical trial.

Safety and Statistical Analysis:

Because of the exploratory nature of Parts A and B of this study, a formal sample size calculation has not been performed. Twenty-four evaluable subjects enrolled in Part B and receiving RV521 or placebo (2:1) at the same

dose level and according to the same dosing regimen for their specified age range group are expected to be sufficient to assess safety, PK and antiviral activity data.

Estimates for total enrolment into Part C are based on a time-weighted average change in RSV log₁₀ viral load from baseline to day 7 in the placebo group of -1.5 log₁₀ vp/ml, with a standard deviation of 1.25. A sample size of 37 per group (total 111 subjects randomised 1:1:1; 2 dose levels of RV521 vs placebo) will provide 90% power to detect at least 1 log₁₀ decrease in the RV521 groups using a 2-sided significance level of 0.05 and assuming a drop out rate of 10%.

Analysis Populations

All safety data analyses will be based on the Safety Population, defined as all subjects who received a single dose (Part A) or any part of any multiple dosing regimen (Parts B and C) of IMP (RV521 or placebo).

The PK population will be defined as all subjects who received RV521 and have at least 1 post-dose PK concentration measured in Parts A, B, or C.

The mITT Population defined in Part A as all subjects enrolled in the study who have an RT-qPCR viral load measurement and/or CBIA, if available, for at least 1 time point including baseline: pre-dose at Dosing Visit 1. In Part B the mITT population will include all subjects who received at least one dose of IMP (RV521 or placebo) and have a pre-treatment positive RSV nasopharyngeal swab confirmed by the central laboratory and agreed by the project team during blind data review. Potential inclusion of subjects who have not completed at least 6 doses of IMP will be decided by the project team during the blind data review meeting. Subjects will be analysed as to their randomised treatment. The mITT population for Part C will include all subjects who receive at least one dose of the study treatments and have a pre-treatment positive RSV confirmed by the central laboratory.

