8.4 Selection of Study Population

8.4.1 Number of Planned Subjects

Approximately 175 subjects (24 subjects in Part A, 40 subjects in Part B, and approximately 111 subjects in Part C) will be evaluated. Eligible subjects ranging in age from ≥ 1 month to ≤ 36 months who are hospitalised because of RSV LRTI will be enrolled in the study. It is anticipated that 102 to 126 subjects will receive RV521 (12 to 24 subjects in Part A, 16 to 28 in Part B, and approximately 74 in Part C), and 45 to 49 subjects will receive placebo (8 to 12 subjects in Part B and approximately 37 in Part C). The total number of subjects to finally be enrolled will depend on the number of DSMC-recommended dosage/dosing regimen adjustments in Parts A and B and whether the DSMC recommend dropping any doses from Part C following their review.

The final number of subjects enrolled in Part C will be dependent upon the number of evaluable subjects and may include any eligible subjects who are in the final stages of screening when the target of 110 enrolled subjects is attained.

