## 6. General Aspects for Statistical Analysis

### 6.1. General Methods

- Unless otherwise specified, summaries for Part A will be presented by cohort, dose level and overall, summaries for Part B will be presented by cohort, treatment, dose level and overall, and summaries for Part C will be presented by treatment and overall.
- Unless otherwise specified, continuous variables will be summarised using the number of observations (n), mean, standard deviation (SD), median, minimum, and maximum. Means and medians will be presented with one more decimal than the observed values. SD values will be presented with 2 more decimals than the observed values.
- Unless otherwise stated, categorical variables will be summarised using number of observations (n), frequency and percentages of subjects.
- Presentations for PK data are described separately in Section 9. Presentations for PD data are described in Section 10.
- All relevant subject data will be included in listings. All subjects entered into the database will be included in subject data listings.
- All statistical testing will be 2-sided with an alpha level of 0.05, with no adjustment for multiple comparisons.
- For Part B, formal statistical testing will focus on the 24 subjects treated at the doses used in Cohort 5 that were identified in Cohorts 3 and 4. These 24 subjects comprise the whole of Cohort 5, plus the 4 subjects from each of Cohorts 3 and 4 that were randomized with the selected dose/placebo.
- Where there are multiple assessments at a given time point, only the results recorded on the scheduled time point page of the case report form (CRF) will be used for summarisation, unscheduled assessments will be listed only.

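### Minor: Part C adds 10% to 34 instead of dividing by 0.9, so if 10% of infants contribute no viral-load data, 37 per arm leaves about 33 evaluable and about 89% power, not 34 and 90%

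*Protocol*

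**What the plan says.** Protocol section 11.2 sizes Part C on the time-weighted average change in log10 viral load from baseline to Day 7, with an SD of 1.25. It states: "A sample size of 34 per group will provide 90% power". The target is a difference of 1 log10 from placebo for each dose level, tested two-sided at 0.05. For drop-outs, "an additional 10% will be added to give group size of 37", which makes 111 over three arms.

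The synopsis (Safety and Statistical Analysis) restates this as a property of the randomised number: 37 per group gives 90% power "assuming a drop out rate of 10" per cent. The Part C design text in the synopsis plans 37 per arm "with an aim to have at least 34 evaluable subjects per treatment group"; sections 8.2 and 8.5.4 repeat that aim.

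Section 8.4.1 plans approximately 111 infants in Part C, but its last paragraph refers to infants still in screening "when the target of 110 enrolled subjects is attained".

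**The concern.** Adding 10% to the required number does not offset a 10% loss, because the loss applies to the larger, randomised number. Rounding 37.4 down widens the gap slightly. If a drop-out is an infant with no usable viral-load data, then 10% loss from 37 does not leave 34, and the synopsis's power statement is a little too favourable.

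These are the stated size and power for the Part C primary endpoint, so they should follow from their own inputs. Nothing else in the design depends on the difference. Separately, the 110 in section 8.4.1 disagrees with the 111 given elsewhere and does not divide equally among three arms (110/3 = 36.7).

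**Working it through.** **Inputs.** Difference 1 log10, SD 1.25, two-sided alpha 0.05, 90% power, 34 per group, 37 randomised per arm (Protocol 11.2); drop-out 10% (synopsis and 11.2). Alpha is not split between the two dose comparisons: SAP section 6.1 tests at 0.05 "with no adjustment for multiple comparisons".

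**Step 1: reproduce 34.** Two-sample t-test with n per group: df = 2n - 2, noncentrality = 1/(1.25 x sqrt(2/n)) = sqrt(n/2)/1.25.

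- n = 34: df 66, noncentrality sqrt(17)/1.25 = 3.30, power 90.2%.
- n = 33: df 64, noncentrality sqrt(16.5)/1.25 = 3.25, power 89.3%.

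So 34 is the smallest t-test n that reaches 90%. The normal approximation would give 2 x (1.960 + 1.282)^2 x 1.25^2 = 32.8, so 33. The protocol's figure is therefore the t-test figure.

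**Step 2: the allowance for loss.**

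- As applied: 34 x 1.10 = 37.4, rounded down to 37.
- To keep 34 after a 10% loss: 34/(1 - 0.10) = 37.8, so 38 per arm (114 in total), leaving 38 x 0.9 = 34.2.
- Left from 37 after a 10% loss: 37 x 0.9 = 33.3.
- Largest loss at which 37 still leaves 34: 3/37 = 8.1%.

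**Step 3: power at what remains.**

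| Evaluable per arm | t-test | Normal approximation |
|---|---|---|
| 33 | 89.3% | 90.1% |
| 33.3 | 89.5% | 90.4% |
| 34 | 90.2% | 91.0% |
| 37 (no loss) | 92.4% | 93.1% |

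With each infant lost at random with probability 10%, t-test power averages 89.4% for 37 randomised per arm and 90.2% for 38.

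**Step 4: how much retained data would close the gap.** Expected drop-outs per arm are 37 x 0.1 = 3.7. Reaching 34 analysed needs 34 - 33.3 = 0.7 of those 3.7, about one in five, to have usable viral-load data.

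**The case against.** A reader might infer that the promised 90% power is missed, or that 34 evaluable, 10% drop-out and 37 randomised are contradictory. The documents do not support either reading, for five reasons.

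- **Drop-out is not the same as non-evaluable.** The Part C mITT population needs one dose and centrally confirmed RSV (Protocol 11.1.1). SAP section 10.2.1 calculates DAVG from whatever post-baseline viral loads exist and excludes only infants with none. The three figures are compatible if about one drop-out in five has a post-baseline swab. Two cautions apply. This SAP describes an older Part C design (1:1, about 120 infants), although its DAVG rule covers Parts B and C and is the only one given. Also, an average over a shortened period is not the full Day 7 quantity.
- **Replacement and flexible enrolment.** Section 8.4.5 lets a Part C infant be replaced if not dosed or if fewer than six doses were completed, and section 8.4.1 ties final enrolment to the number evaluable. Both could recover 0.7 infant per arm. Neither guarantees it: replacement is discretionary and does not reach an infant who took six doses but is not evaluable, and the synopsis describes the cohort as up to 111.
- **Baseline adjustment.** The planned comparison is an analysis of covariance (Protocol 11.1.3), with baseline viral load as a covariate (SAP 10.2.1). If the baseline-outcome correlation were 0.1, 0.2 or 0.3 (assumed; the documents give none), power at 33 per arm would be 89.6%, 90.4% or 91.9%. Section 11.2 claims no such gain, but a weak correlation would be enough.
- **Choice of formula.** The normal approximation gives 90.1% at 33. This shows how small the gap is. It does not rescue the stated pair of figures, because that formula would have required 33 and not 34.
- **Scale.** The 34 is an aim, and 89.5% rounds to about 90%.

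A reader might also infer a larger loss because infants without central RSV confirmation leave the mITT population. The documents give no rate for this, so no figure can be attached to it.

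What stands is the method of inflation, the synopsis sentence that rests on it, and the 110/111 mismatch.

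**Conclusion.** A minor, optional correction. The inflation is wrong in form, and 37 per arm is one short of the 38 that the protocol's own inputs give. If 10% of infants contribute no viral-load data and the comparison is an unadjusted t-test, about 33 per arm remain and power is about 89%. The shortfall is 0.7 infant per arm and about half a point below the stated 90% (89.5% at 33.3; 89.3% at 33). If some drop-outs supply usable swabs, if infants are replaced, or if baseline adjustment removes even a little variance, the shortfall may disappear. The documents do not show that Part C is underpowered, and they do not make more infants necessary. The 110 in section 8.4.1 is a separate clerical mismatch with no bearing on power.

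**What to change.** - **Section 11.2 and the synopsis:** state that 37 per arm gives about 89% power if 10% of infants contribute no viral-load data, and that 34 evaluable per arm (90% power) requires a non-evaluable loss of no more than 3/37 = 8.1%. Expressing the loss as absence of viral-load data, not as drop-out, keeps the sentence consistent with the SAP's DAVG rule.
- **Section 8.4.1:** change the enrolment target from 110 to 111.

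The cost is wording only: no extra infants and no change to design or analysis. One stated power figure becomes up to about a point less favourable. Randomising 38 per arm (114 in total) would also restore the arithmetic, but it adds three infants for under one point of power (89.4% to 90.2% on average) and is not needed.
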